9 PLANNED STATISTICAL METHODS

9.1 General Considerations

The statistical evaluation will be performed using SAS®, version 9.4 or higher.

9.1.1 Stratified Presentation

Sex (male and female) is used as a stratification factor during randomization and for the presentation of descriptive statistics. Race will also be used as stratification factor for the presentation of the descriptive statistics.

9.1.2 Sub-group Analyses

No further sub-group analyses are planned.

9.1.3 Descriptive Statistics

All data will be presented in listings, ordered by randomization arm, subject, and study day unless otherwise specified.

For continuous data, summary statistics will include the number of subjects (n), the number and percent of subjects with missing data, the arithmetic mean, arithmetic standard deviation

Confidentiality Statement

Data and information contained in this document are considered to constitute trade secrets and confidential commercial information, and the legal protections provided to such trade secrets and confidential information are hereby claimed under the provisions of applicable law. No part of this document may be publicly disclosed without the written consent of Philip Morris Products S.A

(SD), 95% confidence interval (CI) of the arithmetic mean, median, first and third quartiles, minimum, maximum; for log-normal data, the geometric mean, geometric coefficient of variation (CV), and 95% CI of the geometric mean will be presented in addition.

Post-baseline summaries will include change from baseline apart from log-normal variables which will percentage change from baseline.

When applicable, the number and percentage of subjects with values below the lower limit of quantification (LLOQ) or above the upper limit of quantification (ULOQ) will also be presented.

For categorical variables frequency counts (n) and percentages (%) will be presented. The number and percentage of subjects with missing data will also be presented.

If the total number of items/events is zero, any further breakdown into sub-categories will not be presented.

Unless specified otherwise the denominator for percentages will be the total number of subjects (n) in each respective group except missing data.

Continuous safety variables (e.g., clinical laboratory values, vital signs, and ECGs) will be reported to the same precision as the source data. Derived variables will be reported using the same precision as the value(s) from which they were derived. For the reporting of descriptive statistics, the mean and median will be reported to 1 decimal place more than the source data; the minimum, and the maximum values will be presented to the same precision as the source data and standard deviations will be reported to 2 decimal places more than the source data.

9.1.4 Definitions for Statistical Data Analysis

At the time of the present protocol, no new terms are defined.

9.1.5 Handling of Dropouts or Missing Data

9.1.5.1 Laboratory Parameters

Values outside detection limits will be substituted using the following rules (e.g., for BoExp parameters):

- Values below LLOQ will be imputed using LLOQ/2.
- Values above ULOQ will be imputed using ULOQ.

Unless otherwise stated, other missing values will not be imputed.

Confidentiality Statement

Data and information contained in this document are considered to constitute trade secrets and confidential commercial information, and the legal protections provided to such trade secrets and confidential information are hereby claimed under the provisions of applicable law. No part of this document may be publicly disclosed without the written consent of Philip Morris Products S.A

1. Questionnaires

Missing data will be handled as follows for the ABOUT – Product Experience Questionnaire.

If there are more than or equal to 50% of within-person item-level missing data within a domain/scale, the missing item-levels will be kept as missing, and the domain/scale score will be set to missing. If there are less than 50% of within-person item-level missing data within a domain/scale, the following rule will be used to produce a complete within-person response pattern:

1. Sum the available within-person item responses and divide that score by the number of items which have responses.
2. Replace the items with missing responses with the within-person mean.
3. Calculate a domain/scale score to two significant digits by using all items and the standard formula used when all items are not missing.

For the Fagerström Test for Nicotine Dependence Questionnaire, the total score is set to missing if any of the items is missing. No imputation of missing value will be done for the Nicotine/Tobacco Product Use History Questionnaire.

2. Missing or Partial Dates

Dates missing or partial will not be imputed for AEs, medical history, and concomitant medications, but the following assumptions will be made to assign them to categories:

Table 11. Missing Date information

Date Information	AE Category	Disease Category	Medication Category
If the date is completely missing, or for partial dates, if the month/year is the same as, or later than the month and/or year of screening	NA	Concomitant Disease	Concomitant Medication
For partial dates, if the month/year is earlier than the month and/or year of screening	NA	Medical History	Prior Medication

Confidentiality Statement

Data and information contained in this document are considered to constitute trade secrets and confidential commercial information, and the legal protections provided to such trade secrets and confidential information are hereby claimed under the provisions of applicable law. No part of this document may be publicly disclosed without the written consent of Philip Morris Products S.A.

3. Insufficient Data for Analysis/Presentation

If there are no values or events for a planned output, the blank TFL shell will be presented with a message printed in the center of the table, such as, “No adverse events related to study procedures occurred for this study”.

For stratified analyses, strata with <5 subjects overall will not be presented.

9.1.6 Handling of Unplanned Data

If any unplanned assessments do occur, they will be included in listings only. Only planned assessments will be summarized.

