### 2.2.3 Anticipated Foreseeable Risks due to Investigational Products

An adult smoker using a THS device or CIG may experience:

- Transient nicotine withdrawal symptoms (e.g., urge to smoke, irritability, anxiety feelings, restlessness, and difficulty to concentrate) as similar to cravings observed during smoking cessation
- Transient symptoms suggesting mild nicotine overdose such as stimulatory effects on sympathetic tone (increased blood pressure, increased heart rate), central nervous system (tremor, blunting of emotions, and decreased ability to concentrate), gastric acid secretion, and vomiting. Individuals who experience adverse events (AEs) (suggesting

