#### 7.3.5 Vital Signs

Vital signs will include systolic and diastolic blood pressure (BP), respiratory rate (RR) and heart rate (HR).

All parameters will be recorded in supine position after the subject has rested for at least 5 minutes. Subjects should have abstained from using any TNP for at least 15 minutes prior to Vital signs assessment.

For those results outside of the normal range, the Investigator will determine appropriate follow-up including reporting of any AEs.

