**Table 9 Time Schedule – Day 1, 2, 3, 4, and 5**

| Time               | Procedures                       | Additional Information |
|--------------------|----------------------------------|------------------------|
| Start of Procedure | Day 1, 2, 3, 4, and 5            |                        |
|                    | Confidentiality Statement |                        |

Data and information contained in this document are considered to constitute trade secrets and confidential commercial information, and the legal protections provided to such trade secrets and confidential information are hereby claimed under the provisions of applicable law. No part of this document may be publicly disclosed without the written consent of Philip Morris Products S.A.

|                         |   |   |
|-------------------------|---|---|
| Prior to breakfast      | Vital signs
COHb in blood  |   |
|                         | Completion of former day urine collection   | Each day of the confinement period  |
|                         | Start of next 24-hour urine collection  | Day 5 collection will be completed in the morning of Day 6, ahead of Discharge  |
|                         | Day 1 only: Inform subjects on allocated study arm  |   |
| During the visit        | Breakfast
Distribution of the THS
Provision of single sticks
Provision of single CIG
Collection of sticks
Collection of CIG butts
Concomitant Medication
Concomitant Diseases
AE/SAE recording
ABOUT–Product Experience
THS product events and THS arms only complaints | Subjects in THS arms
Subjects in THS arms
Subjects in CIG arm
Subjects in THS arms
Subjects in CIG arms
Subjects in THS arms
Subjects in CIG arms
Questionnaire
THS arms only |
| End of visit (11:00 PM) |   | Subjects remain confined  |

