9.6.4.6.4 Vital Signs

Actual values and changes from baseline for pulse rate (bpm), systolic blood pressure (mmHg) and diastolic blood pressure (mmHg), respiratory rate (breaths/min), and body temperature (°C) will be summarized as continuous variables (see section 9.1.3) for the SAF.

Vital signs data will be listed for all subjects.

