9.6.4.6.6 Electrocardiogram

Actual values and changes from baseline for heart rate (bpm), PR interval (msec), QRS interval (msec), QT interval (msec), and QTcF interval (msec) (corrected according to Fridericia's formula) will be summarized as continuous variables (see section 9.1.3) for the SAF.

Each of ECG parameters mentioned above are classified as being normal, abnormal – clinically significant, abnormal – not clinically significant. The numbers and percentages for these categories, including the combined total abnormal classifications, will be summarized at each visit for the SAF, as described in section 9.1.3. as categorical variables.

ECG data will be listed for all subjects.

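### SAP 9.1.6 keeps all unplanned vital-sign and ECG values out of the safety summaries, so an on-product episode measured off schedule is summarised only through AE reporting or the Early termination visit

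*SAP*

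**What the plan says.** SAP 9.1.6 (Handling of Unplanned Data) reads: "If any unplanned assessments do occur, they will be included in listings only. Only planned assessments will be summarized". It has no carve-out for safety data.

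The two sections it affects most are:

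- **Vital signs (SAP 9.6.4.6.4).** The planned output is "Actual values and changes from baseline for pulse rate (bpm), systolic blood pressure (mmHg) and diastolic blood pressure (mmHg"), plus respiratory rate and body temperature, as continuous variables for the safety set. No worst-value row is planned.
- **ECG (SAP 9.6.4.6.6).** Intervals and heart rate are summarised as continuous variables. The counts of normal, abnormal clinically significant and abnormal not clinically significant results "will be summarized at each visit for the SAF". No count over the whole exposure period is planned.

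Both sections also list the data for all subjects.

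Protocol 2.2.3 names, among the transient signs of mild nicotine overdose that THS or cigarettes may cause, "stimulatory effects on sympathetic tone (increased blood pressure, increased heart rate"). Vital-sign and ECG changes from baseline are endpoints of the safety objective (Protocol 3.3, SAP 3.3).

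**The concern.** The effect named in Protocol 2.2.3 is transient. A planned reading shows it only if the reading happens to coincide with it. A reading prompted by symptoms, or a repeat of an out-of-range value, is more likely to coincide, and is by definition unplanned. Protocol 7.3.5 and 7.3.7 leave room for such readings: "For those results outside of the normal range, the Investigator will determine appropriate follow-up including reporting of any AEs".

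Under SAP 9.1.6 those values cannot affect the minimum or maximum in the vital-sign table, or any cell of the ECG abnormality table. What is at stake is how completely two named safety endpoints are described. Efficacy is not affected.

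**Working it through.** No stated figure in the plan depends on this rule, so there is none to reproduce. The check sets the schedule beside the rule.

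**1. Permitted product use (Protocol 4.1).** 06:30 AM to 11:00 PM is 16.5 h a day; 16.5 × 5 days = 82.5 h per subject.

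**2. Planned ECGs (Protocol Appendix A, Tables 8, 10 and 11; SAP 13.1).** Screening, Day -1, Day 6, and Early termination if it occurs.
- Planned on Days 1 to 5 for a subject who completes exposure: 0.
- On Day 6, Protocol 6.2.3 asks subjects to stay abstinent from 11:00 PM on Day 5 until study procedures are complete. If the ECG is taken no earlier than 06:30 AM (assumed; no clock time is given), that is at least 7.5 h without product.
- So for completers the post-baseline ECG table holds no value from the exposure period. An ECG taken in that period is unplanned, unless it belongs to an Early termination visit.

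**3. Planned vital signs (Protocol Table 9, Table 10; SAP 13.1).** One reading on each of Days 1 to 5, in the block before breakfast ("Vital signs COHb in blood"), and one on Day 6: 5 + 1 = 6 for a completer.
- On Day 1 the same block includes telling subjects their arm, so that reading may precede first use.
- On Days 2 to 5 the timing relative to use is open. Breakfast has no clock time, use is allowed from 06:30 AM, and Protocol 7.3.5 requires only 15 minutes without product.

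**4. Applying the rule.**

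| Value | In numeric or normal/abnormal summary? | Other route to a summary |
|---|---|---|
| Planned vital sign or ECG | Yes | – |
| Early termination vital sign or ECG | Yes, it is a planned procedure (Protocol Table 11) | – |
| Unplanned reading, subject symptomatic | No | AE tables; recording the AE is mandatory (Protocol 7.3) |
| Unplanned abnormal reading, no symptoms | No | AE tables, if the investigator reports it (Protocol 8.4 leaves this to discretion) |

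**5. Size if it happens.** 80 subjects randomized 1:1:1:1 gives 80/4 = 20 per arm. Suppose k subjects in an arm have a clinically significant ECG that is unplanned only (k is assumed). The planned table shows 0/20 for them; a count over all readings shows k/20, that is 5% for k = 1 and 10% for k = 2. Suppose instead one subject has planned systolic changes of 0 and an unplanned rise of d mmHg. The mean of a maximum-increase row would then move by d/20: from 0 at d = 0 to 1.5 mmHg at d = 30. Both d and k are illustrative; the documents give no basis for either.

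**The case against.** The case for leaving the rule alone is substantial.

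- **AEs carry the main safety message.** A reader might infer that these episodes never reach a safety summary. The documents do not support that. Protocol 2.2.3 itself treats excessive stimulant effects as adverse events, Protocol 7.3 makes any new untoward occurrence an AE, and SAP 9.6.4.4 makes AEs the primary safety assessment, tabulated by period, severity, relatedness and action taken. This stands. What AE tables lack is the measured change, which is how the endpoints are defined, and the step from an abnormal result to an AE is discretionary under Protocol 8.4.
- **The readings may not exist.** Protocol 6.2.6 calls for a temporary stop of product when overexposure signs appear and asks for no measurement at that moment. Protocol 7.3.5 speaks of follow-up, which need not be a repeat reading. This stands: the number of unplanned readings cannot be estimated.
- **Planned vital signs need not be off product.** A reader might infer that every planned vital-sign reading precedes product use. Before breakfast does not establish that. This also stands, and is why the point rests mainly on ECG.
- **Early termination readings are planned**, so an episode that ends participation can be captured. This stands for those subjects only.
- **Symptom-prompted readings are selective**, and in an open-label study their frequency could differ by arm for reasons other than the product. That is a good reason to keep them out of by-visit summaries, which the fix does. It does not require leaving them out of every summary.
- **Nothing is hidden.** All values are listed, and listings for 80 randomized subjects can be read. True, but listings give no by-arm count.

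One caveat on sources: the SAP follows protocol version 3.0, while the protocol at hand is 2.0. The SAP gives the purpose of that amendment as moving the COHb draw to the evening, and its own schedule shows the same ECG days.

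**Conclusion.** The point holds in limited form. As written, SAP 9.1.6 removes all unplanned vital-sign and ECG values from the numeric and normal/abnormal summaries, and nothing in SAP 9.6.4.6 restores them. An on-product episode measured outside the schedule is then summarised only as an AE or through the Early termination visit. The gap is clearest for ECG, where completers contribute no exposure-period value at all. It is weaker for vital signs, where some planned readings on Days 2 to 5 could follow use.

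The size is one subject in 20 (5 percentage points) in an arm's ECG abnormality count for each affected subject; the number affected is unknown and may be zero. No primary or key secondary result changes. This is a cheap improvement to the description of safety, not the correction of an error in the analysis.

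A reader might extend the argument to spirometry and the laboratory panel. The documents do not support that: the named effect concerns blood pressure and heart rate, and a largest-change summary without a direction would mean little for those parameters.

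**What to change.** Reword SAP 9.1.6 along these lines:

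> *Unplanned assessments are not used in by-visit summaries; unplanned vital-sign and ECG values are included in a worst post-baseline summary for the SAF.*

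Then add, over all planned and unplanned values from first product use on Day 1 to discharge or early termination:

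- to SAP 9.6.4.6.4, one row each for the maximum increase from baseline in systolic blood pressure, diastolic blood pressure and pulse rate;
- to SAP 9.6.4.6.6, the number of subjects with any clinically significant abnormal ECG.

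Footnote both with the number of unplanned readings per arm.

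**Cost.** SAP wording and a few rows in existing tables; no new assessment, and no change to clinical conduct. Product dispensing times are already documented (Protocol 6.5.1), which helps place first use on Day 1. The downside is that subjects with more readings have more chances of an extreme value; the footnote lets the reader judge that. If no unplanned readings occur, the added rows simply summarise the planned values.

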9.1.7 Multiple Comparison/Multiplicity

Overall family-wise type I error will be preserved at the 1-sided α -level of 2.5% (1-sided tests will be conducted for the primary and key secondary study hypotheses). This will be done by using a fixed sequence of testing: primary objective → 1st key secondary objective → 2nd key secondary objective → 3rd key secondary objective → 4th key secondary objective. All objectives will be tested sequentially in a given order at the 2.5% type I error level until one of the objectives is rejected in which case all subsequent testing will be exploratory 2-sided tests at an α -level of 5%, and the associated 2-sided 95% confidence interval will be reported.

The primary study hypothesis will be tested 1-sided with a type I error α -level of 2.5%. The associated 1-sided 97.5% confidence interval will be provided. This will be applied to all BoExps of [Table 1](#) that are part of the primary study hypothesis. Subsequent analyses of objectives will only proceed if this hypothesis is not rejected.

If the primary study hypothesis is not rejected, the same α -level of 2.5% will be used for the 1st key secondary hypothesis and the associated 1-sided 97.5% confidence interval will be reported. This will be applied to all BoExps of [Table 2](#) that are part of the 1st key secondary hypothesis. Subsequent analyses will only proceed if the hypothesis is not rejected.

The analysis will proceed in a similar way for the following key secondary objectives.

For all the exploratory objectives, the statistical tests will be 2-sided with an α -level of 5%. Associated 2-sided 95% confidence intervals will be provided.

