### 12.9.3 Study Significance Level

In this study, the overall familywise type I error will be preserved at the  $\alpha$ -level of 2.5% (1-sided tests will be conducted for the primary and key secondary study hypotheses). This will be done by using a fixed sequence of testing:

- primary objective, then if significant
- 1st key secondary objective, then if significant
- 2nd key secondary objective, then if significant
- 3rd key secondary objective

All objectives will be tested at the 2.5% type I error level until one of the objectives is rejected and no further testing will be performed (in this case, only subsequent exploratory testing will be conducted).

The primary study hypothesis (as assessed using the primary estimand defined in section 12.5.1) will be tested one-sided with a type I error  $\alpha$ -level of 2.5%. The associated 1-sided 97.5% confidence interval will be provided. This will be applied to all BoExp of Table 3 that are part of the primary study hypothesis (every BoExp for each THS arms need to pass for the objective to be considered demonstrated).

If the primary study hypothesis is demonstrated, the same  $\alpha$ -level of 2.5% will be used for the 1st key secondary hypothesis and the associated 1-sided 97.5% confidence interval will be provided. This will be applied to all BoExp of Table 4 that are part of the 1st key secondary study hypothesis (all need to pass for the THS Blade device arm versus CIG for the 1st key secondary objective to be successful).

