9.6.3.1 Key Secondary Objectives

The key secondary objectives are to demonstrate the reduction of additional BoExp to selected HPHC given in [Table 2](#) in smokers who switch from CIGs to THS use compared to those who continue to smoke CIG. The statistical analysis for each of these additional BoExp for each THS arm (THS Blade device, THS Induction Mono device or THS Induction Mid device) will be done similarly to those belonging to the primary objective (except the Success Criteria). More specifically, the analyses described as primary estimand (see section [9.6.1.2](#)) can be repeated, replacing the endpoints listed in [Table 1](#) by those of [Table 2](#) and performing the analysis by THS arm sequentially.

The evaluation of the key secondary objectives will be done using a procedure of fixed sequence testing (see [Figure 2](#)). This first key secondary objective related to the THS Blade device will only be tested if the primary objective is demonstrated for all THS arms. This fixed sequence of study hypotheses ensures that the overall study-wise risk of type I error is preserved at the 2.5%.

If both the primary and first key secondary objectives are declared successful, then the 2nd key secondary objective will be tested with type I error level of 2.5%, this time using the contrast THS Induction Mono device vs. CIG and the BoExp listed in [Table 2](#). If this 2nd key secondary objective is also declared successful, then the 3rd key secondary objective can be tested similarly for the THS Induction Mid device arm. If, along the procedure from the primary objective up to the 3rd key secondary objective, any of the objectives are not declared successful, the sequence testing will stop, and further testing will not be permitted.

Figure 2. Representation of the Procedure of Fixed Sequence Testing

Confidentiality Statement

Data and information contained in this document are considered to constitute trade secrets and confidential commercial information, and the legal protections provided to such trade secrets and confidential information are hereby claimed under the provisions of applicable law. No part of this document may be publicly disclosed without the written consent of Philip Morris Products S.A.

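### SAP 9.1.7 misstates when the fixed sequence may proceed (hypothesis not rejected, instead of objective demonstrated) and lists a 4th key secondary objective that is defined nowhere else

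*SAP*

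**What the plan says.** SAP 9.1.7 sets a familywise level of 2.5% and notes that "1-sided tests will be conducted for the primary and key secondary study hypotheses". It lists the sequence as the primary objective, then the 1st, 2nd and 3rd key secondary objectives, then a "4th key secondary objective". Testing continues "until one of the objectives is rejected in which case all subsequent testing will be exploratory 2-sided tests". On leaving the primary it says "Subsequent analyses of objectives will only proceed if this hypothesis is not rejected". The sentence that passes the alpha to the 1st key secondary opens "If the primary study hypothesis is not rejected, the same", and the same condition is repeated after the 1st key secondary.

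The rest of the plan uses a different condition:

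- SAP 9.6.3.1: "If both the primary and first key secondary objectives are declared successful, then the 2nd key secondary objective will be tested". If, from the primary to the 3rd key secondary, "any of the objectives are not declared successful, the sequence testing will stop, and further testing will not be permitted". The same section requires every BoExp at a level to be significant at 2.5%.
- Protocol 12.9.3 makes each step conditional on significance and passes the alpha on with "If the primary study hypothesis is demonstrated". Protocol 12.6.1 matches SAP 9.6.3.1.
- There are three key secondary objectives in SAP 3.2, SAP 3.5.1 (H2 to H4), SAP section 6, and protocol 3.2 and 12.9.3.
- SAP section 7, which records changes from the protocol, lists none to multiplicity.

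**The concern.** In ordinary usage a significance test rejects a null hypothesis, and rejection is success. On that usage 9.1.7 continues the sequence after a failure and turns everything after a success into exploratory testing. SAP 3.5.1 does give *study hypothesis* another meaning, the reduction itself, but a one-sided test that misses significance has not rejected a reduction. It has only failed to show one.

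What is at stake is which key secondary results may be called confirmatory. SAP 9.1.7 is the SAP's dedicated multiplicity section, and the SAP states no order of precedence between it and 9.6.3.1. In an open-label trial this should not be left to interpretation once results are known.

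**Working it through.** **1. The plan's own figures.** SAP section 6 takes 99% power per objective, assumed independent.

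- Primary over three arms: 0.99^3 = 0.970 (stated: 97%).
- All objectives, counted as three for the primary plus three key secondaries: 0.99^6 = 0.941 (stated: at least 94%).
- With a 4th key secondary: 0.99^7 = 0.932. The stated 94% therefore fits three key secondaries only.

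The 99% input is sound. With 20 per arm and 15% loss (20 × 0.85 = 17), log-scale SD = √ln(1 + GCV²) and a one-sided 2.5% t-test, power is at least 99.7% for every row of SAP Table 7 and at least 99.8% for every row of SAP Table 8.

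**2. Familywise error when moving on requires success.** Take the first objective in the sequence whose null is true. A false claim requires that objective to be declared successful, because nothing later is reached otherwise. All its BoExp must pass at 2.5%, so the probability is at most 2.5%. In 2,000,000 simulated trials, with each level limited by one BoExp at a ratio of 1, the error was 2.5% for both four and five levels. The stated level is reproduced.

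**3. Read literally with the null as the hypothesis.** Testing continues until the first rejection. If the null holds at every level, the chance of at least one false rejection over k independent levels is 1 − (1 − 0.025)^k.

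| Levels | Independent | Correlation 0.5 (assumed, simulated) |
|---|---|---|
| 4 (primary + 3, as defined) | 1 − 0.975^4 = 9.6% | 7.8% |
| 5 (primary + 4, as listed in 9.1.7) | 1 − 0.975^5 = 11.9% | 9.2% |

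These are worst cases: each level is assumed to hinge on a single BoExp with no effect. The comparisons share one CIG arm and the same subjects, so independence overstates them.

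On this reading a significant primary also ends confirmatory testing. SAP section 6 gives primary power both as 97% or more and as at least 99%. The key secondaries would then be confirmatory in at most 1 − 0.97 = 3% of trials on the first figure, or 1 − 0.99 = 1% on the second.

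**4. Read literally with the reduction (H1) as the hypothesis.** The test of GMR ≥ 1 against GMR < 1 has two outcomes. Significance demonstrates the reduction. Non-significance leaves it undemonstrated but not rejected. The 9.1.7 condition is met either way, so a failed primary would not stop the sequence.

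**5. After a failure.** SAP 9.1.7 and protocol 12.9.3 move to exploratory two-sided tests. SAP 9.6.3.1 and protocol 12.6.1 say no further testing is permitted. The two statements agree only if the second means confirmatory testing.

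**The case against.** The best defence is that 9.1.7 never uses the word null. What it speaks of rejecting is an objective or the primary study hypothesis, which SAP 3.5.1 defines as the reduction. Protocol 12.9.3 likewise speaks of testing until an objective is rejected, and there the meaning is plainly *failed*, because the same section moves on only after significance. On that idiom 9.1.7 is loosely worded, not reversed. The correct rule also stands in SAP 9.6.3.1, and SAP 9.6.1.3 refers to 9.6.3.1, not 9.1.7, when it says how the arm contrasts serve the key secondary objectives. Section 7 declares no change. The 4th objective has no hypothesis, endpoints or contrast, so nothing could be tested under it. It may be carried over from another plan, as the unrelated product terms in the SAP abbreviation list suggest.

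Most of this stands. The intended meaning was probably *not failed*, and a statistician working from 9.6.3.1 would apply the right procedure. It does not make 9.1.7 correct. The protocol sets *significant* and *demonstrated* beside its loose phrase. SAP 9.1.7 has neither term, puts *not rejected* where protocol 12.9.3 has *demonstrated*, and uses it three times.

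**Conclusion.** The point holds as a misstated decision rule in the section that claims error control. Neither literal reading of 9.1.7 yields the rule that the rest of the plan uses, and the 4th key secondary objective has no counterpart in either document.

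A reader might go further and infer that the SAP has reversed its testing procedure, or that the trial will run at a familywise error of 9.6% or 11.9%. The documents do not support that. SAP 3.5.1 and the protocol's own idiom allow a charitable reading, SAP 9.6.3.1 states the success rule in full, and the percentages are hypothetical worst cases that need the null reading and independence. Sample size and power are unaffected. The correction should be made, but it does not call the design into question.

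One limit: the protocol reviewed is version 2.0, while the SAP is aligned to version 3.0. SAP 2.1 describes that amendment as a change of the COHb sampling time, so the multiplicity text is assumed to be unchanged.

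**What to change.** In SAP 9.1.7:

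- Replace *not rejected*, at each of its three occurrences, with: demonstrated (null hypothesis rejected at one-sided 2.5% for every BoExp of the current objective).
- Let testing run until one of the objectives is not demonstrated, in place of until one is rejected.
- Delete the 4th key secondary objective.

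In SAP 9.6.3.1, state that after the first objective not demonstrated no further confirmatory testing is permitted and later results are exploratory only, as in SAP 9.1.7 and protocol 12.9.3. Without this step the two SAP sections would still disagree.

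The cost is SAP wording alone, with no change to data collection, sample size or the model. SAP section 2 allows amendments up to database lock.
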